## **4.4 Data Rules**

### **4.4.1 Compliance**

The patient drug intake compliance is calculated as percent of planned tablet intake:

$$100 * \text{Number of taken tablets} / \text{Number of planned tablets}.$$

The *number of planned tablets* is calculated as: *Treatment duration (days) \* Number of planned tablets per day*. The *number of planned tablets per day* is two.

To derive *treatment duration*, the start and stop dates of tablet intake are derived from the collected study treatment exposure (dataset EX). The *number of taken tablets* is derived from the drug accountability (dataset DA).

For patients who withdraw prematurely from the study treatment, compliance will be calculated up to the time of last dose.

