### **5.1.6 Per protocol set (PPS)**

All patients who meet the major inclusion and exclusion criteria at randomization that may affect efficacy, who are not taking excluded concomitant medications during the study that could have an effect on efficacy, have the KCCQ assessed at baseline and at least once during the treatment phase and who are at least 80% compliant with study medication and show no major protocol deviations. The PPS will only be used in the supportive analysis.

Major protocol deviations leading to exclusion from PPS include:

- Overall compliance with study treatment intake of <80% or >120%.
- Study medication was interrupted for more than 10 consecutive days
- No history of chronic heart failure.

A complete list of all validity findings and important protocol deviations leading to exclusion from the PPS will be specified in the Assessment Criteria Identification Requirement (ACIR).

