### 6.1.7 Treatment Compliance

The compliance will be summarized descriptively by treatment group and overall. In addition, compliance will be categorized into three groups (<80%, 80-120%, >120%) and summarized by treatment group and overall.

Compliance will be calculated as the number of tablets taken divided by the number of tablets dispensed \* 100. In addition:

- 1) If the patient is missing return tablets or missing dispensing tablets then those tablets are not counted toward the number of tablets taken for the compliance calculation.
- 2) If the dispensing or return dates are missing but the number of return and dispensing tablets are present, the number of tablets taken will be considered for the compliance calculation.
- 3) Missing compliance will be noted as missing instead of 0.

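### SAP 6.1.7 takes a kit with no return count out of tablets taken but not out of the denominator, so one uncounted 42-day kit puts a fully adherent patient at 75.0%, below the 80% per-protocol cut

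*SAP*

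**What the plan says.** The SAP defines compliance twice.

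- Section 4.4.1 divides tablets taken by planned tablets, where planned tablets are treatment duration in days times a daily number: "The *number of planned tablets per day* is two". Duration comes from the exposure dataset (EX) and tablets taken come from drug accountability (DA). For a patient who stops early, the calculation runs to the last dose.
- Section 6.1.7 uses another denominator: "Compliance will be calculated as the number of tablets taken divided by the number of tablets dispensed".

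Section 6.1.7 then adds three numbered rules. The first reads "If the patient is missing return tablets or missing dispensing tablets then those tablets are not counted toward the number of tablets taken". Rule 3 is that "Missing compliance will be noted as missing instead of 0". None of the three mentions the denominator.

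Section 5.1.6 lists "Overall compliance with study treatment intake of <80% or >120" per cent among the major deviations that lead to exclusion from the PPS. It does not say which formula supplies the figure. Section 6.1.7 also tabulates a <80% class. Protocol 7.7 sets the 80–120% range against scheduled intake.

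**The concern.** When a kit's return count is missing, the tablets used from it are unknown. Rule 1 takes them out of the numerator, and no text takes the same kit out of the denominator. The ratio then treats the kit as not taken at all. A patient who mislaid packaging is scored like one who skipped several weeks of treatment, and with a long kit the shortfall is enough to cross the 80% line.

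Two outputs are exposed. The <80% class in the compliance table would mix low intake with incomplete accountability. The PPS could lose adherent patients for paperwork reasons. Because 4.4.1 and 6.1.7 use different denominators and 5.1.6 names neither, the size of the effect also depends on which formula is programmed.

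**Working it through.** The documents give no worked compliance figure, so there is none to reproduce.

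**Inputs**
- Treatment lasts 24 weeks, or 168 days (Protocol 7.1), at two tablets per day (SAP 4.4.1). Planned tablets = 168 × 2 = 336.
- Drug is dispensed at Visits 2 to 8 (Protocol 7.7). The visit schedule in Protocol 9.1 gives nominal kit lengths of 14, 14, 14, 14, 28, 42 and 42 days, which sum to 168.
- The PPS limit is 80% (SAP 5.1.6).
- Assumptions: the patient takes every tablet, one kit has no return count, timing is nominal and no spare tablets are dispensed.

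**Formula, read literally**

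Compliance = 100 × (336 − 2 × days in the uncounted kit) / 336.

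| Uncounted kit | Counted as taken | Compliance | Against 80% |
|---|---|---|---|
| any 14-day kit (Visits 2–5) | 308 | 91.7% | stays in |
| 28-day kit (Visit 6) | 280 | 83.3% | stays in |
| 42-day kit (Visit 7 or 8) | 252 | 75.0% | out |
| 28-day kit plus one 14-day kit | 252 | 75.0% | out |

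The break-even length is 0.20 × 168 = 33.6 days. In a patient treated for 168 days, only the two 42-day kits cause a failure on their own.

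**Does the kit stay in the denominator?**
- *4.4.1.* Yes. Duration comes from EX, so a gap in DA does not shorten it. This holds whether the return count or the dispensing count is missing.
- *6.1.7, return count missing.* Yes, on the text. The dispensed number is known and no rule removes it, so the result is again 252/336 = 75.0%.
- *6.1.7, dispensing count missing.* No. The kit has no known dispensed number to add, so it drops from both sides and compliance is not lowered.

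**Sensitivity**
- *Visit windows.* Protocol 9.2.9 gives Visit 9 a window of ±7 days. The 42-day-kit result then runs from 70.2% (48-day kit, 161 days on treatment: 113/161) to 80.1% (32-day kit, 161 days: 129/161). The second is the only window combination that reaches 80%. With the ±3 days of the Protocol 9.1 table, the range is 70.9% to 78.9%.
- *Spare tablets (assumption: three spare days per kit).* Tablets dispensed = 2 × (168 + 7 × 3) = 378. With one uncounted 42-day kit, 6.1.7 gives 252/378 = 66.7%. With every kit counted, full adherence gives only 336/378 = 88.9%.
- *Visit 6 supply.* Protocol 9.2.6 describes a six-week interval to Visit 7, but Day 56 to Day 84 is four weeks; the two need reconciling. If 42 days' supply were dispensed there (assumption), tablets dispensed = 2 × 182 = 364, and an uncounted Visit 6 kit would give 280/364 = 76.9% under 6.1.7.
- *Early stopping.* Each kit weighs more. One uncounted 14-day kit in a patient stopping at Day 56 gives 42/56 = 75.0%. The break-even duration for a 14-day kit is 14/0.20 = 70 days.

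**Which denominator fits the 80–120% range?** If tablets taken equal tablets dispensed minus tablets returned, taken/dispensed cannot exceed 100%, so the >120% limit could never apply under 6.1.7. It can apply under planned tablets, which is also how Protocol 7.7 frames the range.

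**After the fix.** Removing the uncounted kit from both sides gives (336 − 84)/(336 − 84) = 252/252 = 100%.

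**The case against.** The strongest reply is that rule 1 is silent on the denominator and does not say that the kit stays in. A sensible programmer could drop it from both sides and obtain 100%. That is true, but the instruction names one side of the ratio only, and neither formula as written removes the kit. A programmer who follows the text gets 75.0%.

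It can also be said that counting only verified intake is a defensible conservative standard for a per-protocol set. That could be chosen on purpose, but the SAP does not state it as a purpose. The same number also feeds the compliance table, where it would be read as low intake.

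Other limits stand. Protocol 7.7 asks patients to return all packaging and sites to explain discrepancies, so missing counts may be few; the documents give no frequency. SAP 5.1 and 5.1.8 leave final set assignment to a validity meeting whose decisions are documented, and 5.1.6 defers the full exclusion list to a separate document. That meeting could rescue such a patient, although the SAP gives it no rule for doing so.

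A reader might infer that rule 3 contradicts rule 1. It does not: rule 3 concerns a compliance value that is missing as a whole, while rule 1 concerns one uncounted kit inside a value that can still be calculated. A reader might also infer that any missing dispensing count lowers compliance. Under 6.1.7 it does not.

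**Conclusion.** The point holds, and it is minor. Followed literally, SAP 6.1.7 rule 1 gives a wrong compliance value for a patient with a missing return count under either of the SAP's two denominators. At nominal timing with no spare tablets, one uncounted kit dispensed at Visit 7 or 8 turns full adherence over 168 days into 75.0%. That meets the <80% exclusion in 5.1.6, subject to the validity meeting. The shorter kits do not do this singly in a patient treated for the full period.

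It would be tempting to conclude that such patients are automatically removed, or that support for the primary result is undermined. The documents support neither. Removal is not automatic, because assignment is settled at the validity meeting. SAP 6.2.3.2 also plans a tipping-point analysis, a repeat on the PEAS, an analysis of assessments before treatment discontinuation on the FAS and PPS, and a missing-at-random analysis; the PPS enters one of these. The primary analysis on FAS (KCCQ) does not use compliance. The number of affected patients is unknown, and nothing in the documents points to a difference between arms.

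**What to change.** 1. State one compliance formula and use it in SAP 4.4.1, in 6.1.7 and for the PPS cut in 5.1.6. Planned tablets fits the Protocol 7.7 reference to scheduled intake and gives the >120% limit a meaning.
2. Amend rule 1 in 6.1.7 so that a kit with a missing return or dispensing count is removed from both numerator and denominator. With planned tablets, this means removing the days that the kit covered.
3. Set compliance to missing when too little of the treatment time is countable. The sponsor should set the minimum before unblinding.
4. State in 5.1.6 that missing counts alone do not exclude a patient from the PPS.

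This takes a few sentences in the SAP and a small programming change, with no new data. The downside is that compliance rests on fewer days for a few patients, and some whose intake cannot be fully verified stay in the PPS.

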### **6.1.8 Completer definition**

A patient is defined as a completer if the following criteria is met:

- On the “End of Treatment” form page of the eCRF, the box corresponding to the question of “Did the subject complete treatment?” is checked off as “Yes.”

## **6.2 Efficacy**

All analyses will be performed according to ITT principle, i.e., including all patients randomized, if not otherwise specified (Section [5.1](#)).

### **6.2.1 Patient Reported Outcomes**

#### **Kansas City Cardiomyopathy Questionnaire (KCCQ)**

The Kansas City Cardiomyopathy Questionnaire (KCCQ) is a self-administered disease-specific measure comprised of 23 items grouped into seven domains (Physical Limitation, Symptom Stability, Symptom Frequency, Symptom Burden, Self Efficacy, Quality of Life and Social Limitations). The following five domains will be considered measures of treatment efficacy:

- Physical Limitation (PLS) (questions 1a to 1f),
- Symptom Frequency (SFS) (questions 3,5,7,9),
- Symptom Burden (question 4,6,8),
- Quality of Life (questions 12,13,14),
- Social limitations (questions 15a to 15d).

The following two KCCQ domains are not considered measures of treatment efficacy and are not included in algorithms for summary scores, these domains will be reported for completeness;

- Symptom Stability (question 2), referred to as ‘change in symptoms’ in the protocol, assesses patient perceived change in symptoms over previous two weeks,
- Self-Efficacy (question 10,11), referred to as ‘self-efficacy and knowledge’ in the protocol, is a quality of care metric assessing patient perceived knowledge of disease management.

For each item, options are on a 5- to 7-point Likert-type scale with varying response options depending on the question. Domain scores are calculated by summing item scores and then

transforming scores to a 0-100 unit scale with higher scores indicating better health status, as described in the KCCQ scoring instruction [10], reproduced in protocol appendix 8.

The individual domain scores will additionally be summarized to three summary scores:

- The Total Symptom Score (TSS) is the mean of the Symptom Burden and the Symptom Frequency scores.
- The Clinical Summary Score (CSS) is the mean of the Total Symptom score and the Physical Limitation score.
- The Overall Summary Score (OSS) is the mean of the Total Symptom score, and the Physical Limitation, Quality of Life, and Social Limitation scores.

The KCCQ will be administered at baseline (visit 2), 2 weeks (visit 3), 6 weeks (visit 5), 12 weeks (visit 7), 18 weeks (visit 8), 24 weeks (visit 9), and safety follow-up (week 28, visit 10); and following premature discontinuation: at time of discontinuation (visit 11) and at 28 +/- 7 days following premature discontinuation (visit 12).

### **EQ-5D-5L**

The EQ-5D-5L is a self-administered generic measure of health-related quality of life which includes five dimensions: mobility, self-care, usual activities, pain/discomfort, and anxiety/depression. Patients provide a rating for each question on a five-level Likert scale: having no problems, having slight problems, having moderate problems, having severe problems and being unable to do/having extreme problems. In addition, patients are asked to self-rate their own health today on a vertical 0-100 unit visual analogue scale (VAS), with 0 corresponding to "the worst health you can imagine", and 100 corresponding to "the best health you can imagine." For the EQ-5D-5L, summary scores will be calculated out of the five dimensions using the preference weighting derived by Craig et al from a representative US general population[19].

The EQ-5D-5L will be administered at baseline (visit 2), 2 weeks (visit 3), 6 weeks (visit 5), 12 weeks (visit 7), 18 weeks (visit 8), 24 weeks (visit 9), and at safety follow-up (week 28, visit 10); and following premature discontinuation: at time of discontinuation (visit 11) and at 28 +/- 7 days following premature discontinuation (visit 12).

### **Patient Global Impression of Change (PGIC) and Patient Global Impression of Severity (PGIS) Questions**

The PGIC contains two questions (i.e. Q1 and Q1a or Q1b):

1. Compared to the start of your treatment, how would you describe your physical limitations due to heart failure today?
  - Response options: "much better", "better", "a little better", "the same", "a little worse", "worse", or "much worse";
  - If a subject responds "much better", "better", or "a little better", then he/she is asked:

- 1a. Was this improvement in your physical limitations an important change for you?
- Response options: “Yes”, “No”.
- If a subject responds “much worse”, “worse”, or “a little worse”, then he/she is asked:
  - 1b. Was this worsening in your physical limitations an important change for you (by important we mean did it bother you)?
  - Response options: “Yes”, “No”.

The PGIS contains 1 question:

- How would you rate your **physical limitations** due to heart failure today?
- Response options: “No Limitations”, “Mild”, “Moderate”, “Severe”, “Very Severe”

These questions will be used to support interpretation of the KCCQ PLS mean change scores.

The PGIC will be administered at 2 weeks (visit 3), 6 weeks (visit 5), 12 weeks (visit 7), 18 weeks (visit 8), 24 weeks (visit 9), and also at safety follow-up (visit 10) and following premature discontinuation; at time of discontinuation (visit 11) and at 28 +/- 7 days following premature discontinuation (visit 12).

The PGIS will be administered at the same timepoints as the PGIC but will be additionally administered at baseline (visit 2).

## 6.2.2 Clinician Reported Outcomes

### Fried frailty score

The Fried frailty phenotype defines 5 key domains for frailty: weakness, low energy, slowed walking speed, decreased physical activity, and weight loss.

The questions patterned from the Fried Frailty score domains are assessed at baseline and at 24 weeks. The questions address five domains of the frailty phenotype: (a) shrinking (weight loss of  $\geq 10$  pounds in the prior year); (b) weakness (decreased or weakened grip strength); (c) exhaustion (fatigue or declining endurance); (d) slowness (slower walking pace); and (e) low activity (decline in physical activity). The 5 questions are as follows:

Within the last 12 months has the patient experienced any of the following?

- Unintentional weight loss ( $\geq 5$  kg/10 lbs).
- Developed decreased grip strength.
- Developed increasing fatigue/lethargy or declining endurance.
- Walks a distance of 5 m/15 feet at a slower pace.

- Decline in typical activity level.

The Fried frailty score will be completed at baseline (visit 2), 24 weeks (visit 9) and at time of premature discontinuation (visit 11).

#### **Assessment of NYHA class**

NYHA class will be assessed according to the classification below:

- Class I: No limitation of physical activity
- Class II: Slight limitation of physical activity in which ordinary physical activity leads to fatigue, palpitation, dyspnea, or anginal pain; the person is comfortable at rest
- Class III: Marked limitation of physical activity in which less-than-ordinary activity results in fatigue, palpitation, dyspnea, or anginal pain; the person is comfortable at rest
- Class IV: Inability to carry on any physical activity without discomfort but also symptoms of heart failure or the anginal syndrome even at rest, with increased discomfort if any physical activity is undertaken

The NYHA class will be completed at baseline and all following visits.

#### **6.2.3 Primary efficacy variable**

##### **6.2.3.1 Primary Analysis of the Primary Efficacy Variable**

The primary endpoint will be change in KCCQ PLS from baseline to week 24.

The estimand of interest is the de facto or treatment policy estimand.

Population: Defined through study inclusion/exclusion criteria (see protocol Section 6.1 and 6.2).

Variable: Change from baseline in KCCQ PLS from baseline to Week 24.

Approach of intervention effect: Regardless of stopping study treatment or adherence to study treatment.

Summary measure: Difference of LS means at Week 24.

The primary analysis will be performed on the FAS (KCCQ) (Section 5.1.2). Missing data will be imputed based on a pattern-mixture model with control-based pattern imputation (Appendix 9.1). The main idea of this method was introduced by Little and Yau (1996) [20] and later refined by Ratitch and O'Kelly (2011) [21]. In this control-based pattern imputation, PROC MI is called in such a way that it builds its imputation model only on data from the control arm, while it imputes missing data in both control and experimental treatment arms using a single control-based imputation model. In other words, the methods will be implemented using copy reference approach. For those patients who had died during the study, they will be imputed with the worst case outcome, i.e., a zero score from the time of death onward.

The analysis of each imputed dataset will be performed using mixed-effects model for repeated measures (MMRM), including treatment, region, heart rhythm, study visit as fixed effects, interaction between study visit and treatment group, and adjustment for the baseline PLS values as covariates. The model will assume an unstructured covariance matrix for within-patient variability.

The model statement is:

$$Y_{ijklm} = \mu + \beta x_i + t_k + r_l + h_m + v_j + (tv)_{jk} + \varepsilon_{ij}$$

where  $Y_{ijklm}$  is the change from baseline in PLS to visit j for patient i;  $\mu$  is the intercept,  $\beta$  is the baseline covariate effect,  $x_i$  is the baseline PLS for patient i,  $t_k$  is the fixed effect of treatment k,  $r_l$  is the fixed effect of region l,  $h_m$  is the fixed effect of heart rhythm m (atrial fibrillation or sinus rhythm from ECG baseline),  $v_j$  is the fixed effect of visit j,  $(tv)_{jk}$  is the interaction effect of treatment k by visit j, and  $\varepsilon_{ij} \sim \text{Normal}(0, \sigma^2)$  represents the residual variance component with  $\text{corr}(\varepsilon_{ij}, \varepsilon_{ij'}) = \rho_{jj'}, j \neq j'$ .

The core SAS-code to be used is the following:

```

proc mixed data=imputed_pls_data;
  by _imputation_;
  class subjldn trt01pn cntygr1n ATRFIBN avisitn;
  model chg= trt01pn cntygr1n ATRFIBN base avisitn avisitn*trt01pn /ddfm=kr outp=resid s
covb;
  repeated avisitn/ subject=subjldn type=un group=trt01pn;
  lsmeans avisitn*trt01pn/e cl diff;
  estimate 'Vericiguat10-Placebo' trt01pn -1 1 0 ;
  estimate 'Vericiguat10-Placebo at Week 2' trt01pn -1 1 0 avisitn*trt01pn -1 0 0 0 0 1 0 0
0 0/e cl;
  estimate 'Vericiguat10-Placebo at Week 6' trt01pn -1 1 0 avisitn*trt01pn 0 -1 0 0 0 0 1
0 0 0/0/cl;
  estimate 'Vericiguat10-Placebo at Week 12' trt01pn -1 1 0 avisitn*trt01pn 0 0 -1 0 0 0 0
1 0 0/0/cl;
  estimate 'Vericiguat10-Placebo at Week 18' trt01pn -1 1 0 avisitn*trt01pn 0 0 0 -1 0 0 0
0 1 0/0/cl;
  estimate 'Vericiguat10-Placebo at Week 24' trt01pn -1 1 0 avisitn*trt01pn 0 0 0 0 -1 0 0
0 0 1/0/cl;

  estimate 'Vericiguat15-Placebo' trt01pn -1 0 1;
  estimate 'Vericiguat15-Placebo at Week 2' trt01pn -1 0 1 avisitn*trt01pn -1 0 0 0 0 0 0 0
0 0 1 0 0 0 0/e cl;
  estimate 'Vericiguat15-Placebo at Week 6' trt01pn -1 0 1 avisitn*trt01pn 0 -1 0 0 0 0 0
0 0 0 0 1 0 0 0/0/cl;
  estimate 'Vericiguat15-Placebo at Week 12' trt01pn -1 0 1 avisitn*trt01pn 0 0 -1 0 0 0 0
0 0 0 0 1 0 0/0/cl;
  estimate 'Vericiguat15-Placebo at Week 18' trt01pn -1 0 1 avisitn*trt01pn 0 0 0 -1 0 0 0
0 0 0 0 0 0 1 0/0/cl;
  estimate 'Vericiguat15-Placebo at Week 24' trt01pn -1 0 1 avisitn*trt01pn 0 0 0 0 -1 0 0
0 0 0 0 0 0 1/0/cl;

RUN;

```

Results of the MMRM analysis on 100 separately imputed datasets can now be combined to derive an overall result. This is done by applying PROC MIANALYZE with the following generic code:

```
ods output parameterestimates=mi_lsmean;
proc mianalyze parms=lsmean;
  by trt01pn avisitn;
  modeffects trt01pn*avisitn;
RUN;
```

Based on the responder definitions obtained from anchor-based analysis (Section 4.3.2), a responder is defined as a patient whose improvement from baseline in KCCQ PLS is greater than or equal to responder definition. The number of responders at each visit will be summarized and tested using a chi-square test. Note that missing data will not be imputed in the responder analysis. In addition, the number of patients with KCCQ PLS improvement from baseline by >5 points at 24 weeks and other thresholds (e.g. >3, >7, >10, >15, >20) will be summarized for each arm and assessed using a chi-square test. The number of patients with KCCQ PLS decline from baseline by >5 points and other thresholds (>3, >7, >10, >15, >20) at 24 weeks will be summarized by each arm and examined using a chi-square test as well. Further, PDF and CDF of change from baseline at 24 weeks for KCCQ PLS domain will be plotted to compare the proportion of patients who are meeting certain threshold from vericiguat and placebo arms. The Kolmogorov–Smirnov test will be performed to determine if the curves are significantly different.

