10.4 Determination of sample size

The sample size estimation for this study will be based on the analysis of the primary endpoint of KCCQ PLS at 24 weeks comparing vericiguat 15 mg versus placebo and 10 mg versus placebo, to achieve 80% power with two-sided alpha level of 0.05 to detect a treatment difference from placebo in one or both of the dose groups. A mean difference from placebo in KCCQ PLS of 5 points for both dose groups and a common SD of 21 points are assumed. Under the same assumption of treatment effect and standard deviation, the power to detect

difference for any single comparison will be 65%. The 80% power was based on an “either or” success criterion, i.e., if at least one of the primary null hypotheses is rejected. The marginal power to reject any single comparison is 65%.

The given sample size provides 97% power to detect +30 m placebo-corrected increase in the secondary endpoint 6MWT (assumed SD 80 m) for any one dose group, and 80% power to detect an increase by +22.3 m, which is below the 35 m increase associated with a 6.2 point improvement in KCCQ PLS at 24 weeks in FAIR-HF and greater than the 15 m increase at 3-months that was associated with a 2.3 point improvement in KCCQ PLS in ACTION-HF (34).

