A 5 point improvement in KCCQ OSS in patients with HFrEF is considered to represent a clinically significant change in heart failure status (35). Similarly, a change of +6.4 and -5.1 points in KCCQ PLS were associated with either small improvements or small deteriorations in clinical status, as determined by a cardiologist, in the Cardiovascular Outcomes Research Consortium study cohort in patients with HFrEF (35, 36). In addition, baseline KCCQ PLS score has also been associated with peak VO₂ and distance traveled on the 6 minute walk test (6 MWT), with 6.4 and 7.5 point differences in PLS being associated with 1SD changes for peak VO₂ and 6 MWT respectively (37). Furthermore, both anchor-based and distribution-based analyses of the SOCRATES-PRESERVED data support an improvement of 5 points in KCCQ PLS as MCID. This effect size has been proposed to the US FDA during a Type C meeting and was considered preliminarily acceptable pending additional data analyses (see Section 10.5) per Agency correspondence following the meeting. As such, this study will be powered to detect a placebo-corrected change of at least 5 point improvement in KCCQ PLS from baseline to 24 weeks. An SD of 21 points was assumed based on studies in which KCCQ PLS has been reported in the literature (38-43). The patients will also be followed until the end of the study regardless of stopping study treatment or not, hence the drop-out rate is considered negligible. Based on these considerations, the total sample size will be N=735 with N=245 each in the placebo, 10 mg vericiguat arm and 15 mg vericiguat arm in a 1:1:1 randomization.

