### 6.2.5 Multiplicity adjustment

The study uses the graphical method of Maurer and Bretz [22] to provide strong multiplicity control across the primary KCCQ PLS hypotheses and the secondary 6 MWT hypotheses. The overall two-sided alpha level will be controlled at 0.05. The two primary hypotheses will be tested using the Bonferroni procedure, each at a splitted level of alpha 0.025. The two secondary hypotheses will be tested based on a parallel gatekeeping principle. As shown in Figure 6-1, if the test of both primary and secondary endpoints at one of the dose groups is significant at the alpha level of 0.025, the primary and secondary endpoint at the other dose group can be tested at the alpha level of 0.05, in an ordered manner. Figure 6-1 shows the  $\alpha$ -allocation for each hypothesis in the circle representing the hypothesis.

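### The primary KCCQ PLS model fits one baseline slope to all five visits; if that slope changes over time, the week-24 contrast is valid but less precise than it could be, and one extra model term removes the loss

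*SAP*

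**What the plan says.** SAP 6.2.3.1 describes the model as containing treatment, region, heart rhythm, visit, "interaction between study visit and treatment group, and adjustment for the baseline PLS values as covariates". In the equation the baseline term is βx_i, with no visit index. The code agrees: "model chg= trt01pn cntygr1n ATRFIBN base avisitn avisitn*trt01pn". Treatment is crossed with visit; baseline is not. The within-patient covariance is unstructured, and the code fits it separately by arm. The summary measure is the difference in LS means at week 24.

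Protocol 10.3.1 has the same single baseline term, so the SAP does not depart from the protocol here. The supportive analyses in SAP 6.2.3.2 (tipping point, PEAS, before treatment discontinuation, and without imputation) all reuse the primary model, and SAP 6.2.4 carries the approach over to 6MWT. No planned analysis lets the baseline slope vary by visit.

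On power, Protocol 10.4 sizes the trial "to achieve 80% power with two-sided alpha level of 0.05" for success on at least one dose. It assumes "A mean difference from placebo in KCCQ PLS of 5 points for both dose groups and a common SD of 21 points" and sets "N=735 with N=245 each in the placebo, 10 mg vericiguat arm and 15 mg vericiguat arm in a 1:1:1 randomization". It adds: "The marginal power to reject any single comparison is 65" (per cent).

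**The concern.** The outcome is change from baseline. With similar SDs at each visit, the slope of change on baseline at visit j is about r_j − 1, where r_j is the correlation of that visit's score with baseline. If r_j falls over time, the slope becomes steeper (more negative). A shared slope is a precision-weighted average of the visit slopes. It leans toward early visits, where less variance is left after conditioning on baseline, so it is too shallow for week 24.

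Some such fall is plausible here. Patients may be randomized before discharge from, or up to six months after, a decompensation, so for some of them baseline is a transient state. This is an expectation, not something the documents show.

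The unstructured covariance does not repair the problem, because baseline enters as a covariate and not as one of the repeated responses. The imputation code in SAP Appendix 9.1 regresses each visit on baseline and the earlier scores. It therefore already allows visit-specific baseline effects that the analysis model then rules out.

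What is at stake is precision at the one tested visit, not validity.

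**Working it through.** **1. The plan's own power figures.** Inputs: 245 per arm, difference 5, SD 21 (Protocol 10.4). For alpha, SAP 6.2.5 says "The overall two-sided alpha level will be controlled at 0.05" and tests the two primary hypotheses "each at a splitted level of alpha 0.025".

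- Standardised difference: 5 / (21 × √(2/245)) = 2.635. The two-sided 0.025 critical value is 2.241.
- Single-comparison power: Φ(2.635 − 2.241) = 65.3% (stated: 65%).
- At-least-one power, with correlation 0.5 between the tests from the shared placebo arm: 80.6% (stated: 80%).

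Both figures reproduce.

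**2. Degrees of freedom.** SAP Appendix 9.1 lists five post-baseline PLS visits, so visit-specific slopes add 5 − 1 = 4 parameters. The protocol synopsis omits week 18 from its list of visits, but the visit schedule and the SAP include it.

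**3. Formula for the loss.** Let β be the vector of visit slopes and S the residual covariance given baseline. With complete (imputed) data, the shared slope is b = (1′S⁻¹β) / (1′S⁻¹1). The week-24 contrast then has variance (2/n) × [S₂₄ + (b − β₂₄)² × Var(baseline)]. The relative inflation is

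(b − β₂₄)² × Var(baseline) / S₂₄.

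With SDs equal over time and scaled to 1, β_j = r_j − 1 and S₂₄ = 1 − r₂₄².

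**4. Assumptions.** The documents give no baseline SD, baseline-to-visit correlation or visit-specific slope. Assumed: r falls linearly from week 2 to week 24, and the residual correlation is the same between all visits.

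**5. Worked case: r from 0.80 to 0.60, residual correlation 0.5.**

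- Slopes: −0.200, −0.236, −0.291, −0.345, −0.400.
- Weights in b: 0.421, 0.292, 0.167, 0.087, 0.033. Week 24 carries about 3% of the weight.
- b = −0.245, so the gap from the week-24 slope is 0.155.
- Inflation: 0.155² / 0.64 = 3.7%.

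**6. Range of week-24 variance inflation.** The 6MWT column uses weeks 12 and 24 only.

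| r, week 2 to week 24 | Residual corr. 0.4 | 0.5 | 0.6 | 0.7 | 6MWT, 0.4 to 0.7 |
|---|---|---|---|---|---|
| 0.60 to 0.60 | 0% | 0% | 0% | 0% | 0% |
| 0.70 to 0.60 | 0.6% | 0.6% | 0.7% | 0.8% | 0.1–0.2% |
| 0.75 to 0.60 | 1.5% | 1.7% | 2.0% | 2.5% | 0.3–0.4% |
| 0.80 to 0.60 | 3.2% | 3.7% | 4.6% | 6.0% | 0.7–0.9% |
| 0.85 to 0.60 | 6.2% | 7.3% | 9.1% | 12.1% | 1.2–1.7% |

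An inflation of k means that the extra term recovers k/(1 + k) of the planned model's variance; for 12.1% this is 10.8%. A steeper fall, 0.85 to 0.50, gives 13.7% to 22.4% inflation for residual correlation 0.5 to 0.7, so the top of the table is not a ceiling.

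**7. Simulation check.** 4,000 trials per scenario, 245 per arm, unstructured covariance, shared slope against visit-specific slopes:

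- Mean week-24 effects of the two models agreed within 0.01 point, and model standard errors were close to the empirical SDs in both.
- Variance recovered was −0.2% with a flat correlation of 0.70; 3.4% for 0.80 to 0.60; and 6.6% for 0.85 to 0.60 (both with residual correlation 0.5). The formula gives 0%, 3.6% and 6.8%.

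**8. Power, as illustration only.** If SD 21 is the residual SD under the planned model and 7% of the variance were recovered, SD becomes 21 × √0.93 = 20.25. Single-comparison power moves from 65.3% to 68.8%, and at-least-one power from 80.6% to 83.4%.

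**The case against.** The strongest reply is that this is a preference about efficiency, not an error. The contrast is unbiased under either model, its standard errors are honest, and the SAP follows the protocol's equation. All of that stands. A reader might infer that the primary test is biased or invalid; neither the model nor the simulation supports that.

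Second, the falling correlation is assumed. That also stands. With a constant slope the gain is zero, and with a modest fall (0.70 or 0.75 to 0.60) it is at most about 2.5%.

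Third, a reader might take the 65% single-comparison power as a shortfall that the term would repair. The documents do not support this. The design criterion is rejecting at least one hypothesis, planned at 80%, and that figure reproduces. Nor does the protocol say whether SD 21 is before or after baseline adjustment. If it is before, the model as written already exceeds 65%: in the simulated 0.85 to 0.60 case (residual correlation 0.5), single-comparison power is 71.6% as written and 74.7% with the term.

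Fourth, a reader might carry the PLS gain over to 6MWT. Protocol 9.2.7 and 9.2.9 schedule 6MWT on treatment only at weeks 12 and 24, so no early visit pulls the shared slope away. Protocol 10.4 also gives 6MWT 97% power for a 30 m difference. Little is to be gained there.

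What survives is narrower: the term costs almost nothing, and no planned analysis includes it.

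**Conclusion.** The point holds as a low-cost improvement in precision for KCCQ PLS. The single slope in the equation and code, its reuse in every supportive analysis, and the cost of 4 degrees of freedom follow directly from the documents. The size does not. It rests on assumed correlations and is about 0.6% to 12% of the week-24 variance for a fall from 0.70–0.85 to 0.60 with residual correlation 0.4 to 0.7. It is zero if the slope is constant and larger if the fall is steeper, so no single percentage should be read as a documented figure or an upper bound. For 6MWT the same assumptions give at most about 1% to 2%. Validity and the stated power are not in question.

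**What to change.** Before unblinding, add `base*avisitn` to the MODEL statement in SAP 6.2.3.1, and give the baseline coefficient a visit index in the equation. The supportive analyses that reuse the model should carry the same term. The treatment ESTIMATE statements need no change, because the new term does not involve treatment. SAP 7.1.1 now reports no changes from the protocol; the addition should be recorded there, since Protocol 10.3.1 has the single slope.

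Cost: one model term and 4 degrees of freedom, negligible with about 735 patients. If the slopes turn out constant, almost nothing is lost (0.2% of variance in the simulation). For 6MWT the term costs 1 degree of freedom and is optional, for consistency only.
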